### 3.2.5 *PD Population*

The PD Population is defined as all randomized patients who met enrollment criteria, who receive at least one dose of study drug, have a baseline PK assessment, and have a baseline *E. coli* measurement at or above  $1 \times 10^3$  Colony-Forming Unit (CFU)/mL. The PD Population will be the primary population for analysis of all PD-related secondary and exploratory endpoints.

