### 3.2.4 *PK Population*

The PK Population is defined as all patients who receive at least one dose of LBP-EC01 and have at least one measurable post-dose concentration of LBP-EC01. The PK Population will be the population for all PK analysis.

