### 3.4.1 Sample Collections for Pharmacokinetic Analysis

Blood and urine samples for PK will be collected at the times specified in Schedule of Blood and Urine Sampling of the Protocol (Table 2).

Pre-dosing PK samples for urine and blood will be collected after catheterization (if there is no existing catheter), up to 30 minutes prior to dosing. Post-dosing PK samples will be taken within 60 minutes after the catheter is released and re-clamped for 20 minutes to take additional urine and blood samples. 6 hour timepoint ( $\pm 1$  hour) will be collected after 6 hours following the AM dose

Of note, urine PK data will not include volumes since a 20 mL aliquot is taken rather than the whole void urine volume. Patients are allowed to urinate freely outside of the specified collections.

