### 3.4.2 Handling Missing or Below the Lower Limit of Quantification Data

Blood and urine PK data will follow the same rules for handling of missing or below limit of quantification (BLQ) data.

For PK concentration data, if the actual sampling time is missing, but a valid concentration value has been measured, the concentration value will be flagged and the scheduled time point may be used for the calculation of PK parameters.

In cases of missing pre-dose for the first dose of each treatment period, the missing components may be assumed as zero. For the other cases, the missing data will not be imputed.

For semi-log plots, zero and BLQ values will be imputed as "0.1" for graphical purposes.

For the individual concentration and PK parameter calculation of each treatment period, the following rules will be applied:

- If one or more BLQ values occur before the first measurable concentration, they will be assigned a value of zero.
- If BLQ values occur between measurable concentrations in a profile, the BLQ should be omitted (set to missing).
- If BLQ values occur after the last measurable concentration in a profile, the BLQ should be omitted (set to missing).

For the concentration summary and mean concentration plot preparation of each treatment period, the following rules will be applied:

- Mean concentration at any individual time point or defined time interval will only be calculated if at least half of the patients have valid values (i.e., quantifiable and not missing) at this time point or defined time interval for each treatment period
- In cases where a mean value is not calculated due to the above criterion not being met, the value will be set to missing
- BLQ values will be set to zero.

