#### 3.4.3 *Pharmacokinetic Concentration*

LBP-EC01 concentrations will be determined in both blood and urine by using a plaque forming assay and expressed in units of plaque forming units (PFU)/mL.

Actual sampling times that are outside the sampling time windows may be excluded from concentration summary and mean concentration plotting but will still be used in the calculations of PK parameters and individual concentration plotting.

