### 3.5 Pharmacodynamic Assessment

The secondary endpoints concern the pharmacodynamics of LBP-EC01. These will be summarized by treatment based on the PD Population.

*E. coli* assessments will be made at the timepoints specified in the SoA of the protocol. Incidence of the following endpoints will also be summarized with counts and percentages of patients at Day 1 (Baseline), Day 2, Day 3, Day 5, Day 7 (EOT), Day 14 and Day 28:

- Reduction in urinary *E. coli* burden at timepoint from Baseline
- Biological elimination of *E. coli* at timepoint after Baseline. Biological elimination is defined as measurement below  $1 \times 10^3$  CFU/mL

The following *E. coli* parameters will be derived based on all available post-Baseline data and summarized and listed:

- Time to 1 log reduction in urinary *E. coli* from Baseline
- Biological elimination at any timepoint.
- Incidence and time to recurrence of *E. coli* colonization. Recurrence is defined as past biological elimination followed by increase above the patient's baseline CFU/mL.
- Incidence of infection based on clinical signs and symptoms defined as an adverse event marked as a UTI symptom and followed by antibiotic use.

*E. coli* parameters will be summarized first for the total CFU/mL in a patient (sum of CFU/mL for all *E. coli* strains) but may also be summarized by strain specific *E. coli* colonization (individual strain CFU/mL per patient).

All *E. coli* assessment data will be listed.

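### The PD Population requires a baseline PK assessment that none of the E. coli or infection endpoints uses, so patients with valid PD data can be left out of the primary PD analysis

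*SAP*

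**What the plan says.** Section 3.2.5 sets four conditions for the PD Population. The patient must have met the enrollment criteria, must be someone "who receive at least one dose of study drug, have a baseline PK assessment", and must have a baseline E. coli count of at least 1 x 10^3 CFU/mL. The PK condition stands apart from the E. coli condition. The section goes on: "The PD Population will be the primary population for analysis of all PD-related secondary and exploratory endpoints". Section 3.5 says of the secondary endpoints: "These will be summarized by treatment based on the PD Population".

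What a PK assessment is follows from section 3.4.3: "LBP-EC01 concentrations will be determined in both blood and urine by using a plaque forming assay", in PFU/mL. On timing, section 3.4.1 says: "Pre-dosing PK samples for urine and blood will be collected after catheterization (if there is no existing catheter), up to 30 minutes prior to dosing".

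The PK sections are more lenient about the same value. Section 3.4.2 reads: "In cases of missing pre-dose for the first dose of each treatment period, the missing components may be assumed as zero". Section 3.2.4 defines the PK Population as "all patients who receive at least one dose of LBP-EC01 and have at least one measurable post-dose concentration of LBP-EC01", with no baseline condition.

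**The concern.** An analysis set should be defined by what its endpoints need. Here the set for the E. coli and infection endpoints depends on a pre-dose phage measurement that does not enter any of them, and the SAP gives no reason for it. The value is optional in the PK analysis, where it is used, and mandatory in the PD analysis, where it is not.

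At stake is the completeness of the primary analysis of the secondary endpoints in a trial of 36 patients. A patient excluded by this rule has no assigned place elsewhere for these endpoints: section 3.2.2 keeps the ITT Population for endpoints that are not PD-related, and section 3.2.3 does the same for the Evaluable Population.

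**Working it through.** **Step 1. Does any endpoint in section 3.5 use a phage concentration?**

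| Endpoint | Data it needs | Pre-dose PFU/mL used? |
|---|---|---|
| Reduction in E. coli burden | Baseline and visit CFU/mL | No |
| Biological elimination | CFU/mL against 1 x 10^3 | No |
| Time to 1 log reduction | Baseline and serial CFU/mL | No |
| Recurrence of colonization | Elimination, then CFU/mL against baseline | No |
| Infection | UTI-symptom adverse event, then antibiotic use | No |

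The baseline that the count endpoints do need is already secured by the E. coli threshold in 3.2.5.

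**Step 2. Could the condition screen out pre-existing phage?** No. It asks only that the assessment exists and says nothing about its result.

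**Step 3. Compare the rules for one missing first pre-dose PK value.**
- PK parameter calculation (3.4.2): the value may be set to zero.
- PK Population (3.2.4): membership is unaffected.
- PD Population (3.2.5): the patient is excluded.

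**Step 4. Size.** Section 2.2.4 gives 36 patients at 2:1. The SAP states no alpha, power or effect size, so there is no sample-size calculation to reproduce.
- LBP-EC01 arm: 36 x 2/3 = 24. One exclusion = 1/24 = 4.2%.
- Placebo arm: 36 x 1/3 = 12. One exclusion = 1/12 = 8.3%.

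The SAP gives no rate of missing pre-dose samples. For illustration only, assume a rate m, the same in both arms and independent between patients. The expected loss is 36m, and the chance of losing at least one of n patients is 1 - (1 - m)^n.

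| Assumed m | Expected loss of 36 | P(at least one of 36) | P(at least one of 12 placebo) |
|---|---|---|---|
| 0% | 0 | 0% | 0% |
| 2% | 0.72 | 1 - 0.98^36 = 52% | 1 - 0.98^12 = 22% |
| 5% | 1.8 | 1 - 0.95^36 = 84% | 1 - 0.95^12 = 46% |
| 10% | 3.6 | 1 - 0.90^36 = 98% | 1 - 0.90^12 = 72% |

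These figures count patients without a baseline PK assessment. The patients wrongly lost are those among them who meet the other PD conditions, so the table is an upper limit at each assumed rate.

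**The case against.** **The loss may be nil.** Pre-dose blood and urine samples are planned for everyone shortly before dosing. If all are obtained, nobody is excluded. This stands: the rates in the table are assumptions and are no evidence that samples will be missed.

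**The data are not wholly discarded.** All E. coli data are listed (3.5). Section 3.6.1, on the ITT and Evaluable Populations, allows an optional overall summary of all bacteria that includes E. coli. UTI signs and symptoms are also reported as adverse events of special interest in the Safety Population (3.7.1). This stands in part, but none of these outputs reproduces the PD endpoints. Section 3.2.5 calls the PD set primary rather than sole, yet no second set is named for them.

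**PK may be a slip for PD.** That is possible. The phrase would then largely repeat the baseline E. coli condition, and deleting it would resolve either reading.

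**Stronger readings that a reader might infer, and that the SAP does not support:**
- *The whole placebo arm could fall out.* This needs two things the SAP does not say: that placebo samples go unassayed, and that an assessment means an assay result and not a collected sample. Section 3.4.1 collects pre-dose samples with no limit by arm, and section 3.5 plans PD summaries by treatment. Placebo patients are outside the PK Population, but 3.2.5 does not refer to that population.
- *The loss would be unequal by arm.* The sample precedes the first dose in a double-blind trial, so its collection should not depend on treatment. Without the unassayed-placebo assumption, only chance imbalance remains.
- *Every PD secondary endpoint is affected.* Immunoglobulin changes are listed as a PD endpoint in 2.3.2 but are analyzed in 3.7.3, under the Safety Population rule of section 3.7. The SAP is inconsistent here, so the point is secure only for the E. coli and infection endpoints.

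**Conclusion.** The point holds for the E. coli and infection endpoints. Section 3.2.5 contains a condition with no stated purpose and no role in those endpoints. Applied literally, it removes patients with usable data from their primary analysis. This rests on the SAP text alone and needs no assumption about missing-sample rates.

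The cost is 4.2% of the LBP-EC01 arm or 8.3% of the placebo arm per patient excluded. The number excluded cannot be determined from the SAP and may be zero. The analyses are descriptive (3.1.5), so no test or error rate is affected. The defect should be corrected, but it does not threaten the study.

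**What to change.** Before unblinding, delete the baseline PK assessment condition from section 3.2.5 and keep the baseline E. coli threshold. The timing matters because sections 3.2.3 and 5.2 require only Evaluable status to be settled before the treatment codes are opened; they set no such deadline for PD membership.

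Do not put a requirement for post-baseline E. coli data in its place. That would be a post-randomization condition, which treatment can influence, whereas the present one is at least pre-treatment.

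The cost is an edit to the SAP wording. The protocol was not among the documents reviewed, and section 7 declares no changes from it apart from COVID-19. If the protocol has the same PD definition, the edit is a departure that must be recorded in section 7. That is a small downside: one documented change.

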### 3.2.6 *Subgroup Analyses*

Subgroup analyses of these Analysis populations may also be performed. Such subgroups include, but are not limited to:

- Patients with indwelling catheterizations and patients with intermittent catheterizations
- Patients with *E. coli* sensitive to LBP-EC01 and patients with *E. coli* insensitive to LBP-EC01

## 3.3 Subject Data and Study Conduct

### 3.3.1 *Subject Disposition*

Counts and percentages of patients who were screened (signed informed consent), discontinued early during screening (screen failures), and randomized will be summarized in total based on all screened patients.

Counts and percentages of patients who were randomized, discontinued early from the study, and completed the study will be summarized by treatment and in total based on all randomized patients. Reasons for early discontinuation will also be summarized.

The disposition data, including screen failure reasons, will also be listed.

### 3.3.2 *Protocol Deviations*

Counts and percentages of patients with protocol deviations by deviation category will be summarized by treatment and in total based on all randomized patients and listed.

#### 3.3.2.1 *Eligibility Criteria*

Eligibility criteria (inclusion/exclusion) will be listed based on randomized patients.

### 3.3.3 *Analysis Populations*

Counts and percentages of patients in each analysis population will be summarized by treatment and in total based on all randomized patients. Reasons for exclusion from each analysis population may also be summarized. Data will be listed including randomization data.

### 3.3.4 Demographic and Baseline Characteristics

The following demographic and baseline characteristics will be summarized:

- Age (years) at enrollment
- Sex
- Childbearing potential
- Race
- Ethnicity
- Height (cm)
- Weight (kg)
- Body mass index (BMI) (kg/m^2)
- Frequency and timing (within 1 month of Screening, within 1 year of Screening) of prior UTI
- Prior antibiotic use (within 30 days of Screening)
- Catheter use at Screening (none, indwelling, intermittent, other)

Demographic and baseline characteristics will be summarized with descriptive statistics or counts and percentages of patients as appropriate by treatment and in total for all randomized patients and each defined analysis population. Data will also be listed.

### 3.3.5 Medical History

Medical history will be coded to system organ class and preferred term using the Medical Dictionary for Regulatory Activities (MedDRA) version 22.0. Counts and percentages of patients with medical history by system organ class and preferred term will be summarized by treatment and in total based on all randomized patients. Data will also be listed.

### 3.3.6 Prior and Concomitant Medications

Medications will be coded to anatomical therapeutic chemical (ATC) class and preferred term using the WHO Drug Dictionary version March 2019G B3. For summary purposes, medications will be considered prior medications if they stopped prior to the first dose of study drug and concomitant medications if they were taken at any time after the first dose of study drug (i.e., started prior to the first dose of study drug and were ongoing or started after the first dose of study drug).

If a medication has incomplete start or stop dates, dates will be imputed to determine whether a medication should be considered prior and/or concomitant. If a medication start date is incomplete, the first day of the month will be imputed for missing day and January will be imputed for missing month. If a medication stop date is incomplete, the last day of the month will be imputed for missing day and December will be imputed for missing month. Incomplete start and stop dates will be listed as collected without imputation.

Counts and percentages of patients taking prior and concomitant medications by ATC class and preferred term will be summarized by treatment and in total based on the Safety Population. Data will also be listed.

### 3.3.7 Catheterization

Catheter use from screening through the End of Study will be logged. All catheter data will be listed for the Safety Population.

### 3.3.8 Study Drug Administration and Exposure

Days of exposure to study drug will be calculated as date of last dose of study drug – date of first dose of study drug + 1. Days of exposure to study drug and number of doses received will be summarized by treatment based on the Safety Population with descriptive statistics and with counts and percentages of patients. Study administration data will be listed.

## 3.4 Pharmacokinetic Assessment

Of note, systemic absorption of LBP-EC01 may not occur due to the local route of administration and consequently, may result in little to no quantifiable LBP-EC01 concentrations in the blood for a subject's PK profile.

### 3.4.1 Sample Collections for Pharmacokinetic Analysis

Blood and urine samples for PK will be collected at the times specified in Schedule of Blood and Urine Sampling of the Protocol (Table 2).

Pre-dosing PK samples for urine and blood will be collected after catheterization (if there is no existing catheter), up to 30 minutes prior to dosing. Post-dosing PK samples will be taken within 60 minutes after the catheter is released and re-clamped for 20 minutes to take additional urine and blood samples. 6 hour timepoint ( $\pm 1$  hour) will be collected after 6 hours following the AM dose

Of note, urine PK data will not include volumes since a 20 mL aliquot is taken rather than the whole void urine volume. Patients are allowed to urinate freely outside of the specified collections.

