#### 2.2.3 *Study Drug*

LBP-EC01 is a clear to opalescent, colorless to slightly yellow, aqueous solution. LBP-EC01 is a mixture of 3 crPhages internally named as p0031-8, p00ex-2, p004k-5, which are derived from wild-type myoviridae phages that target *E. coli*. These phages have been engineered to contain

an identical CRISPR-Cas3 construct and have been combined in equal amounts at  $1 \times 10^6$  –  $1 \times 10^{12}$  PFU/mL (equivalent to approximately  $1.5 \times 10^7$  –  $1.5 \times 10^{13}$  PFU/vial). One vial of LBP-EC01 containing approximately 15 mL of solution will be steriley mixed with 45 mL of Lactated Ringer's solution (injection, USP) by the site pharmacy prior to each dose administered (details will be included in the pharmacy manual). LBP-EC01 and placebo solutions will be indistinguishable.

LBP-EC01 will be administered by bladder instillation via a newly placed urinary catheter BID at the maximum feasible dose, based on the manufacturing process (approximately  $1.5 \times 10^7$  –  $1.5 \times 10^{13}$  PFU/vial), totaling approximately 60 mL of solution via sterile catheter tipped syringe (details will be included in the pharmacy manual). The urinary catheter will be clamped and the solution left in situ for a minimum of 30 minutes (to a maximum of 40 minutes) following instillation and then it will be placed on free drainage (duration of clamp should be documented).

LBP-EC01 will be provided in a 20 mL vial containing approximately 15 mL of the crPhage cocktail. This vial will be brought to room temperature prior to mixing with 45 mL of Lactated Ringer's solution (injection, USP) under sterile conditions and placed into a sterile syringe with a catheter tip. Handling and mixing of the vials making up LBP-EC01 will be done by the unblinded study pharmacist (details are provided in the pharmacy manual). Placebo solution Lactated Ringer's solution (injection, USP) will be brought to room temperature and will also be prepared by the pharmacist under aseptic technique and placed into a sterile catheter tipped syringe. The unblinded pharmacist will use the IVRS system to determine the randomization allocation.

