**Blood and Urine PK Parameters:**

Parameters	Description
$C_{\max, \text{Dose 1}}$	Maximum concentration; determined directly from the concentration time profile; if the maximum concentration occurs at more than one time point, $C_{\max}$ is defined as the first maximum value
$T_{\max, \text{Dose 1}}$	Time to $C_{\max}$ of the first dose; determined directly from the concentration-time profile
$AUC_{0-t}$	Area under the concentration vs time curve (AUC) from predose (time 0) to the last quantifiable concentration ( $C_{\text{last}}$ ) for Dose 1
$C_{\text{trough,max}}$	Minimum measured concentration from Day 1 (only including predose #2) through Day 7
$C_{\max, \text{all}}$	Max post-dose concentration determined from Day 1 through Day 7
$AI_{\text{trough}}$	Accumulation index using $C_{\text{trough}}$ (predose Day 7 / $C_{\text{trough,max}}$ )

The actual collection times will be used for the calculation of PK parameters. The Linear-Log Trapezoidal method (equivalent to the Linear Up/Log Down option in WinNonlin) will be used in the computation of all AUC values.

Additional PK parameters may be determined as appropriate.

The blood and urine PK parameters will be listed and summarized by treatment using descriptive statistics for the PK Population.

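### The SAP computes urine Dose 1 AUC from a zero predose value and reads urine Cmax and Tmax from post-drainage samples, as for blood, although the dose is instilled into the bladder

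*SAP*

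**What the plan says.** Dosing is described in SAP section 2.2.3: "LBP-EC01 will be administered by bladder instillation via a newly placed urinary catheter BID". A vial of about 15 mL is mixed with 45 mL of diluent, "totaling approximately 60 mL of solution via sterile catheter tipped syringe". Then "The urinary catheter will be clamped and the solution left in situ for a minimum of 30 minutes", up to 40 minutes, after which the catheter goes on free drainage and the clamp duration is documented.

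Section 3.4.1 refers to protocol Table 2 for the sampling times and adds: "Post-dosing PK samples will be taken within 60 minutes after the catheter is released and re-clamped for 20 minutes". The only other post-dose time it states is 6 hours (±1 hour) after the morning dose. Urine volumes are not part of the PK data.

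Section 3.4.2 gives blood and urine the same rules: "If one or more BLQ values occur before the first measurable concentration, they will be assigned a value of zero". A missing first predose value may also be taken as zero.

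Section 3.4.4 has a single parameter table for both matrices. Dose 1 Cmax is "Maximum concentration; determined directly from the concentration time profile", Tmax is read from the same profile, and AUC0-t runs from predose (time 0) to the last quantifiable value. Every AUC uses linear-up/log-down interpolation. There is no separate rule for urine.

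**The concern.** For blood, starting at zero and rising to the first measured value is a sensible reading of a drug that must first be absorbed. For urine it is not. The drug is in the bladder at full instilled strength from the moment of dosing, and the first sample described comes after most of it may have drained away. The planned rule therefore interpolates upward from zero over the interval in which the product is deliberately held at its site of action.

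Section 2.3.1 places urine within the PK assessment under the primary endpoints, and section 3.4 expects little or no quantifiable phage in blood. Urine may therefore supply most of the PK results. A reader of the report could take urine Cmax and AUC0-t as peak and total bladder exposure, when they leave out or distort the dwell. Differences between patients could then reflect how well the catheter drained and when the sample was drawn.

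**Working it through.** **1. The plan's own dose figures.** Strength is 1×10⁶ to 1×10¹² PFU/mL in about 15 mL (section 2.2.3).
- Per vial: 10⁶ × 15 = 1.5×10⁷ and 10¹² × 15 = 1.5×10¹³ PFU, as stated.
- Instilled volume: 15 + 45 = 60 mL, as stated.
- Instilled concentration C0 = PFU per vial / 60 mL = 2.5×10⁵ to 2.5×10¹¹ PFU/mL, if the bladder is empty. Urine already present would lower it.

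**2. When the first post-dose urine is taken.**
- Earliest: 30 min dwell + 20 min re-clamp = 50 min after instillation.
- Latest: 40 + 60 = 100 min if the 60 minutes run from release, or 40 + 20 + 60 = 120 min if they run from the end of the re-clamp.

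**3. The first AUC segment, with no pharmacological assumption about size.** Let the first sample be C1 at time t1. From zero at time 0, linear-up gives ½·C1·t1. If concentration does not rise before t1, it is at least C1 throughout, so the true area is at least C1·t1. The planned segment is then at most half the truth. It equals half only when there is no dilution or drainage effect at all (C1 = C0).

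**4. Size with a well-mixed bladder.** Assumed, not in the SAP: urine inflow q = 0.5 to 2 mL/min and volume left after drainage R = 5 to 30 mL. With dwell Tc (minutes) and prompt re-clamp:
- End-of-dwell concentration: Ce = C0·60/(60 + q·Tc)
- Dwell area: C0·(60/q)·ln[(60 + q·Tc)/60]
- First sample: C1 = Ce·R/(R + 20q)
- Re-clamp area: Ce·(R/q)·ln[(R + 20q)/R]

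Example with Tc = 30, q = 1, R = 10:
- Ce = 0.667 C0 and C1 = 0.222 C0.
- True area is 0.406 + 0.122 = 0.528 C0·h.
- Planned triangle is ½ × 0.222 × 50/60 = 0.093 C0·h, or 17.5% of the truth.

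Over the whole grid (Tc = 30 or 40), the triangle captures about 5% to 37% of the true area to the first sample, and C0/C1 is 1.7 to 21. With Tc = 40 and 40 minutes of free drainage before re-clamping, it captures 23% or less.

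**5. Size over the dosing interval, with a simpler model.** Assumed: dwell of 0.5 h at C0, residual fraction r from drainage to a first sample at 1 h, then exponential decline with rate k to 12 h.
- Planned AUC = r·C0·S, where S = 0.5 + (1 − e^(−11k))/k
- AUC with the dwell = 0.5·C0 + r·C0·S
- Ratio = 1 + 0.5/(r·S)

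S is 1.94, 3.32 and 5.41 h for half-lives of 1, 2 and 4 h.

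| r | first hour (1 + 1/r) | 0-12 h, half-life 1 h | 2 h | 4 h |
|---|---|---|---|---|
| 0.5 | 3 | 1.5 | 1.3 | 1.2 |
| 0.1 | 11 | 3.6 | 2.5 | 1.9 |
| 0.01 | 101 | 27 | 16 | 10 |

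The entries are the factors by which the planned AUC is too low.

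**The case against.** Several points on the other side stand.

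- **Table 2 is not at hand.** The full sampling schedule is in the protocol. The wording of section 3.4.1 puts post-dose samples after release, but a dwell-phase urine sample in Table 2 would reduce the bias.
- **Cmax is defined as the observed maximum.** It is computable as written, and the SAP never says that it represents concentration during the dwell. A reader might infer that reported urine Cmax is an erroneous figure, low by 1/r. The documents do not support that. It is a correctly computed post-drainage maximum under a label that does not say so.
- **The primary endpoint is worded more narrowly.** Section 2.3.1 lists Cmax, Tmax and AUC0-t for blood. Urine belongs to the PK assessment there, but these three parameters reach urine only through the table in section 3.4.4. It would be too strong to say that a named primary parameter fails.
- **Phage can multiply.** Patients are colonized with the target organism, so a real later peak is possible and Tmax is not always an artefact.
- **The multiples are conditional.** r, half-life, R and q have no source in the SAP.
- **Consequences are limited.** PK is descriptive, no hypothesis is tested, and section 3.4.3 already summarizes, lists and plots urine concentrations by time.

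None of this repairs the first AUC segment. Section 3.4.4 does qualify its parameters as applying where appropriate, but it gives no rule for when a urine parameter is not.

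**Conclusion.** The point holds as a fault in the stated calculation and in the labels. Applied to urine, the rules in sections 3.4.2 and 3.4.4 draw AUC0-t as a ramp from zero over a period when the bladder holds the instilled dose.

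That first segment is at most half the true area, provided concentration does not rise before the first sample and none is taken during the dwell. Over 0-12 h the shortfall is about 1.2-fold to 27-fold across the assumed values. The upper end needs r = 0.01 with the shortest half-life, so the range shows sensitivity and is not an estimate for this trial. Urine Cmax is a maximum post-drainage concentration, and urine Tmax largely reflects the schedule unless phage grow in the bladder.

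Blood parameters are unaffected.

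**What to change.** Split the parameter table in section 3.4.4 by matrix.

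- **Blood:** leave as written.
- **Urine maximum:** label it *maximum observed post-drainage concentration*.
- **Urine time of maximum:** report it only as the observed sampling time, with a note that the dwell is not sampled. This keeps any later peak from phage growth visible.
- **Urine AUC:** compute it from the first post-drainage sample to the last quantifiable sample and label it *post-drainage AUC*, or drop it. Do not start it from a zero predose value.
- **Dwell exposure:** an AUC that sets the dwell to the nominal instilled concentration should be at most a labelled supplementary calculation. With r = 0.01 in the model above, that unmeasured constant makes up 90% to 96% of the total (0.5/0.554 and 0.5/0.519), so it would mainly restate dose and clamp time.

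If Table 2 does include a urine sample during the dwell, say so in section 3.4.1 and adapt the labels.

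The cost is SAP wording and a small programming change, with no new samples. The drawback is that the post-drainage AUC excludes exposure during the dwell, and its label must say so. It also starts at a different time in each patient, so the start time should be listed.
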